16.1.4 Estimation of Pharmacokinetic Parameters

The computer program Phoenix® WinNonlin® version 6.4, or higher (Certara, L.P., Princeton, New Jersey, USA) will be used to derive PK parameters applying non-compartmental analysis (NCA).

The statistical software SAS® (Statistical Analysis System, SAS-Institute, Cary NC, USA, windows version 9.4 or higher) may be used to generate additional PK parameters, produce tables, listings and figures.

16.1.4.1 Estimation of Pharmacokinetic Parameters in Plasma

PK parameters will be calculated using the actual elapsed time since dosing, given with a precision of 4 decimal places or the SAS format Best12. In cases where the actual sampling time is missing, calculations will be performed using the scheduled time. Otherwise, there will be no further imputation of missing data.

The following PK parameters will be calculated where appropriate from xevinapant and its metabolite D-1143-MET1 plasma concentrations:

Symbol	Definition
$AUC_{0-t_{last}}$	The area under the concentration-time curve (AUC) from time zero (= dosing time) to the last sampling time (t_{last}) at which the concentration is at or above the lower limit of quantification. Calculated using the mixed log-linear trapezoidal rule (linear up, log down).
$AUC_{0-\infty}$	The AUC from time zero (dosing time) extrapolated to infinity, based on the predicted value for the concentration at t_{last} , as estimated using the linear regression from λ_z determination. $AUC_{0-\infty} = AUC_{0-t} + C_{last\ pred} / \lambda_z$.
AUC_{0-24}	The area under the concentration-time curve (AUC) from time zero (= dosing time) to 24 hours. Calculated using the mixed log-linear trapezoidal rule (linear up, log down).
$AUC_{extra\%}$	The AUC from time t_{last} extrapolated to infinity given as percentage of $AUC_{0-\infty}$. $AUC_{extra\%} = (\text{extrapolated area} / AUC_{0-\infty}) * 100$.

Symbol	Definition
CL/F	The apparent total body clearance of study intervention following extravascular administration, taking into account the fraction of dose absorbed. $CL/F = \text{Dose}_{p.o.} / AUC_{0-\infty}$ (xevinapant only).
C_{max}	Maximum observed concentration.
t_{max}	The time to reach the maximum observed concentration collected during a dosing interval (unless otherwise defined, take the 1 st occurrence in case of multiple/identical C_{max} values).
t_{last}	The last sampling time at which the concentration is at or above the lower limit of quantification.
C_{last}	The observed concentration at the last sampling time (t_{last}) at which the concentration is at or above the lower limit of quantification.
$t_{1/2}$	Apparent terminal half-life. $t_{1/2} = \ln(2) / \lambda_z$.
λ_z	Terminal first order (elimination) rate constant. Determined from the terminal slope of the log-transformed concentration curve using linear regression on terminal data points of the curve.
V_z/F	The apparent volume of distribution during the terminal phase following extravascular administration, based on the fraction of dose absorbed. $V_z/F = \text{Dose} / (AUC_{0-\infty} * \lambda_z)$ following single dose (xevinapant only).
MR($AUC_{0-t_{last}}$)	Metabolic ratio of $AUC_{0-t_{last}}$. $AUC_{0-t_{last}}$ for D-1143-MET1 divided by the $AUC_{0-t_{last}}$ of xevinapant corrected for MW. $MR(AUC_{0-t_{last}}) = AUC_{xevinapant} * MW_{xevinapant} / AUC_{D-1143-MET1} * MW_{D-1143-MET1}$ where $MW_{xevinapant} = 561.71 \text{ g/mol}$ $MW_{D-1143-MET1} = 476.61 \text{ g/mol}$
MR($AUC_{0-\infty}$)	Metabolic ratio of $AUC_{0-\infty}$. $AUC_{0-\infty}$ for D-1143-MET1 divided by the $AUC_{0-\infty}$ of xevinapant corrected for MW. $MR(AUC_{0-\infty}) = AUC_{xevinapant} * MW_{xevinapant} / AUC_{D-1143-MET1} * MW_{D-1143-MET1}$ where $MW_{xevinapant} = 561.71 \text{ g/mol}$ $MW_{D-1143-MET1} = 476.61 \text{ g/mol}$
MR(C_{max})	Metabolic ratio of C_{max} . C_{max} for D-1143-MET1 divided by the C_{max} of xevinapant corrected for MW. $MR(C_{max}) = C_{max,xevinapant} * MW_{xevinapant} / C_{max,D-1143-MET1} * MW_{D-1143-MET1}$ where $MW_{xevinapant} = 561.71 \text{ g/mol}$ $MW_{D-1143-MET1} = 476.61 \text{ g/mol}$

Partial areas should be calculated using the nominal dosing interval. The actual dosing interval calculated from case report form (CRF) time data should not be used.

The following PK parameters will be calculated for diagnostic purposes and listed, but will not be summarized:

- First ($\lambda_{z \text{ low}}$) and last ($\lambda_{z \text{ up}}$) time point of the time interval of the log-linear regression to determine λ_z .
- Number of data points (N_i) included in the log-linear regression analysis to determine λ_z .
- Goodness of fit statistic (adjusted Rsq) for calculation of λ_z .
- Span ratio.

The regression analysis should contain data from at least 3 different time points in the terminal phase consistent with the assessment of a straight line on the log-transformed scale. Phoenix WinNonlin “best fit” methodology will be used as standard. However, in some cases, further adjustment may be made by the pharmacokineticist, if warranted, after agreement with the Sponsor. The last quantifiable concentration should always be included in the regression analysis, while the concentration at t_{max} and any concentrations <LLOQ which occur after the last quantifiable data point should not be used.

If $\text{AUC}_{\text{extra}\%} > 20\%$ and/or the coefficient of correlation (Rsq adj) of λ_z is < 0.8 and/or the observation period over which the regression line is estimated is less than two-fold the resulting $t_{1/2}$, the rate constants and all derived parameters (e.g. $t_{1/2}$, $\text{AUC}_{0-\infty}$, CL/F etc.) will be listed, flagged and included in the parameter outputs and may be excluded from descriptive statistics.

In case profiles have a measurable pre-dose concentration less than or equal to 5% of its C_{max} value, the participant’s data without any adjustments will be included in all PK measurements and calculations. If the pre-dose value is greater than 5% of the C_{max} , the participant will be dropped from all PK evaluations. However, this participant’s data will be flagged and reported.

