**9.4.3.1 Pharmacokinetic Analyses**

Endpoint	Statistical Analysis Methods
Primary: Xevinapant AUC 0-tlast , AUC 0-∞ , and C max	PK parameters and calculation method are in Section 8.4 . Summary statistics will be provided by ethnic group and overall for the PK analysis set.
Secondary: Xevinapant AUC 0-24 , t max , t 1/2 , CL/F, Vz/F	PK parameters and calculation method are in Section 8.4 . Summary statistics will be provided by ethnic group and overall for the PK analysis set.
Secondary: D-1143-MET1 AUC 0-tlast , AUC 0-24 , AUC 0-∞ and C max , t max , and t 1/2 , xevinapant: D-1143-MET1 molar ratio AUC 0-tlast , AUC 0-∞ , and C max	PK parameters and calculation method are in Section 8.4 . Summary statistics will be provided by ethnic group and overall for the PK analysis set.

In addition, the ratio of PK parameters between the ethnic categories from this study and from historical data from healthy participant studies in non-Asian participants may also be estimated. These integrated analyses across studies will be specified in a separate Integrated Analysis Plan and not included in the CSR.

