Generally, the term ‘participant’ will be used instead of ‘subject’ or ‘patient’. However, in tables and listings the term ‘subject’ will be used to match CDISC requirements, except for in-text tables where ‘participant’ will be used to match the CSR and protocol templates. Similarly, the term ‘study intervention’ will be used in this document instead of ‘treatment’ to match protocol and CSR templates, however, tables and listings will use ‘treatment’ for brevity reasons. Exceptions from this rule are commonly used terms like “on-treatment”, “treatment-emergent”, “treatment policy”, “subject-years”, “by-subject”, or names of eCRF pages like “Treatment Termination” page.

5 Objectives and Endpoints

Objectives	Endpoints	IAP section
Primary		
To characterize the xevinapant PK after a single 200 mg dose in healthy East Asian participants and in healthy Japanese participants	Xevinapant AUC _{0-last} , AUC _{0-∞} , and C _{max}	16.1
Secondary		

Objectives	Endpoints	IAP section
To evaluate the safety and tolerability of a single 200 mg dose of xevinapant in healthy East Asian participants and in healthy Japanese participants	Occurrence of TEAEs (incidence, frequency, intensity and causality), occurrence of changes in safety laboratory assessments, 12-lead ECGs, and vital signs	15
To determine additional plasma PK parameters of xevinapant after a single 200 mg dose in healthy east Asian participants and in healthy Japanese participants	Xevinapant AUC ₀₋₂₄ , t _{max} , t _{1/2} , CL/F, and V _Z /F	16.1
To characterize the PK of metabolite D-1143-MET1 after a single 200 mg dose in healthy East Asian participants and in healthy Japanese participants	D-1143-MET1 AUC _{0-last} , AUC ₀₋₂₄ , AUC _{0-∞} , C _{max} , t _{max} , and t _{1/2} , D-1143-MET1/xevinapant molar ratio for AUC _{0-last} , AUC _{0-∞} , C _{max}	16.1

6 Overview of Planned Analyses

All final, planned analyses identified in the IAP will be performed only after the last participant has completed the last visit, i.e. Follow-up/Discontinuation visit with all study data in-house, all data queries resolved, and the database locked.

There are no planned formal interim analyses.

Statistical analyses will be performed on the basis of CDISC SDTM data. These SDTM data contain as clean as possible eCRF data as well as external data including pharmacokinetic data.

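### The SAP's three metabolic-ratio formulas are inverted and mis-apply the molecular-weight correction, so none of them yields the D-1143-MET1/xevinapant molar ratio named as a secondary endpoint

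*SAP*

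**What the plan says.** SAP Section 5 lists as a secondary endpoint the "D-1143-MET1/xevinapant molar ratio for" AUC0-tlast, AUC0-∞ and Cmax. Protocol Sections 1.1 and 3 state the same ratio in the same direction.

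SAP Section 16.1.4.1 has one row for each of the three ratios, and each row holds a verbal definition, a formula and the two molecular weights.

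- **Words.** The AUC0-tlast row describes the parameter "for D-1143-MET1 divided by the $AUC_{0-t_{last}}$ of xevinapant corrected for MW"; the Cmax row describes it "for D-1143-MET1 divided by the C_{max} of xevinapant corrected for MW". The AUC0-∞ row is worded the same way. All three say metabolite over parent.
- **Formulas.** Both AUC rows give "AUC_{xevinapant} * MW_{xevinapant} / AUC_{D-1143-MET1} * MW_{D-1143-MET1". The Cmax row gives "C_{max,xevinapant} * MW_{xevinapant} / C_{max,D-1143-MET1} * MW_{D-1143-MET1". All three put parent over metabolite.
- **Constants.** "MW_{xevinapant} = 561.71" and "MW_{D-1143-MET1} = 476.61", both in g/mol.

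The analysis table in Protocol Section 9.4.3.1 names the quantity "xevinapant: D-1143-MET1 molar ratio", which is the opposite direction to Protocol Section 3. SAP Section 7 declares no change from the protocol's planned analyses.

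**The concern.** Each row of the SAP contradicts itself: the words give metabolite over parent and the formula gives parent over metabolite. The molecular-weight term does not rescue the formula as a parent/metabolite ratio, because each exposure is multiplied by its own molecular weight where a mass-to-molar conversion divides by it. The missing brackets add a third problem, since software evaluates a × b / c × d from left to right.

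These rows are the only place where the calculation is specified. Protocol Section 8.4.2 assigns metabolic ratios to SAS, but its parameter table has no entry for them. A programmer who turns to Protocol Section 9, on which SAP Section 4 says the plan is based, finds the parent-first label in 9.4.3.1 and may take it as confirmation of the inverted formula.

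At stake are three stated secondary endpoints. Protocol Section 2.1 gives as purposes of the study the comparison of PK between East Asian subgroups and with earlier data in Caucasian participants. An inverted ratio would show a higher metabolite share in one group as a lower one.

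**Working it through.** The documents give no numerical molar ratio, so there is no figure to reproduce. The check is algebraic.

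**Inputs**
- Molecular weight of xevinapant 561.71 g/mol and of D-1143-MET1 476.61 g/mol (SAP 16.1.4.1).
- X and M: the same PK parameter (AUC0-tlast, AUC0-∞ or Cmax) for xevinapant and D-1143-MET1. Mass units are assumed, since molar units would need no molecular-weight correction.
- R = M/X, the mass ratio. Protocol Section 2.2 says only that the two exposures are of similar order, so R from 0.1 to 10 is an assumed range.

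**Constants**
- 561.71 / 476.61 = 1.1786
- 476.61 / 561.71 = 0.8485
- (561.71 / 476.61)² = 1.389
- 561.71 × 476.61 = 267,717

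**The endpoint.** Each mass exposure becomes molar on division by its own molecular weight:

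(M / 476.61) / (X / 561.71) = R × 561.71 / 476.61 = 1.1786 R

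**The SAP formula, denominator bracketed**

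(X × 561.71) / (M × 476.61) = 1.1786 / R

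Against the endpoint this is wrong by a factor of (1.1786 / R) / (1.1786 R) = 1/R².

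**Is that a valid inverse?** The xevinapant/D-1143-MET1 molar ratio is (X / 561.71) / (M / 476.61) = 0.8485 / R. The bracketed formula exceeds it by 1.1786 / 0.8485 = 1.389, or 38.9%, at every R.

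**The SAP formula, left to right**

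((X × 561.71) / M) × 476.61 = 267,717 / R

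This is 267,717 times the uncorrected xevinapant/metabolite mass ratio. Relative to the endpoint the factor is (561.71 × 476.61 / R) / (R × 561.71 / 476.61) = 476.61² / R² = 227,157 / R².

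| R (assumed) | Endpoint, 1.1786 R | Bracketed, 1.1786 / R | Bracketed ÷ endpoint | Left to right |
|---|---|---|---|---|
| 0.1 | 0.118 | 11.786 | 100 | 2,677,166 |
| 0.5 | 0.589 | 2.357 | 4.00 | 535,433 |
| 0.9 | 1.061 | 1.310 | 1.23 | 297,463 |
| 1.0 | 1.179 | 1.179 | 1.00 | 267,717 |
| 1.1 | 1.296 | 1.071 | 0.83 | 243,379 |
| 2.0 | 2.357 | 0.589 | 0.25 | 133,858 |
| 10 | 11.786 | 0.118 | 0.01 | 26,772 |

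**Comparison between groups.** Both readings are a constant divided by R, so a ratio of geometric means between two groups is exactly inverted. If one group's true ratio is 1.3 times the other's, the formula reports 1 / 1.3 = 0.77.

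**The case against.** **One slip, not two.** For the metabolite/parent direction the required factor is 561.71 / 476.61, and the bracketed formula already contains it. Swapping only the two exposure terms and adding brackets repairs everything. This is right as an account of how the error may have arisen. The molecular-weight term is wrong only for the ratio the formula actually writes down, parent over metabolite. As printed, though, the expression is still a molar ratio in neither direction.

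**The correct words stand beside each formula.** A wrong result follows only if the formula is coded and the words are ignored. That is true, but the formula is the part written to be programmed, and the protocol's analysis table points in the formula's direction.

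**The error may be small or obvious.** Under the bracketed reading it vanishes at R = 1 and is +23% at R = 0.9 and −17% at R = 1.1. The fourfold figures rest on assumed values of R. The left-to-right reading gives values so large that review would catch them, and its missing brackets could come from a stacked fraction flattened in the PDF text. All of this is fair. Lost brackets cannot, however, explain xevinapant in the numerator of all three rows. The bracketed reading is the more dangerous one, because its values look plausible.

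**The damage is recoverable.** Under the bracketed reading the correct value is 1.389 divided by the reported value. The geometric mean, its confidence interval, and the minimum and maximum therefore convert exactly, and the geometric CV does not change. Individual parameters are listed, and no hypothesis test uses the ratio. This limits the consequence, but arithmetic means and SDs do not convert this way, and a reader must first notice the error.

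**Conclusion.** The concern holds. All three formulas contradict their own verbal definitions and the endpoint, and neither reading yields a molar ratio in either direction. With brackets the result is wrong by a factor of 1/R², from 100-fold too high to 100-fold too low over the assumed range of R from 0.1 to 10. It agrees with the endpoint only where a participant's R is exactly 1. Without brackets it is wrong for every participant, by 227,157 / R². Either way, comparisons between groups are reversed.

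The size depends on R, which the documents do not give, and on concentrations being in mass units. If they were molar, no molecular-weight term would be needed and the formula would still be inverted. The error reaches the results only if the formula is programmed as printed. The xevinapant primary endpoints and the safety analyses are not touched. Because three secondary endpoints have no usable computational definition, this must be corrected before programming.

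**What to change.** In SAP Section 16.1.4.1, replace the three formulas with

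MR(P) = (P for D-1143-MET1 / 476.61) / (P for xevinapant / 561.71) = (P for D-1143-MET1 × 561.71) / (P for xevinapant × 476.61)

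for P = AUC0-tlast, AUC0-∞ and Cmax, keeping the brackets explicit.

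Change the label in Protocol Section 9.4.3.1 to the D-1143-MET1/xevinapant direction, to agree with Protocol Section 3 and SAP Section 5.

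The SAP change is three lines and affects neither data collection nor participants. The protocol label is a single phrase, but Appendix 2 requires a protocol amendment to be documented and approved by the IRB/IEC. If an amendment for this alone is not wanted, a sentence in SAP Section 7 stating the direction used and noting the inconsistent label would settle the analysis until the protocol is next amended.

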16.1.5 Statistical Analysis of PK Parameter Data

No formal statistical analysis of PK parameter data is planned.

16.1.6 Presentation of PK Concentration and PK Parameter Data

16.1.6.1 Listings and Tables

The following PK tables will be produced based on the PK Analysis Set:

- Descriptive statistics of concentrations by analyte and ethnic group (Japanese, non-Japanese East Asian and overall)
- Descriptive statistics of PK parameters by analyte and ethnic group (Japanese, non-Japanese East Asian and overall)

The following PK listings will be produced based on the Safety Analysis Set:

- Individual concentrations by analyte and ethnic group
- Individual PK parameters by analyte and ethnic group
- Individual diagnostic PK parameters by analyte and ethnic group
- PK Sampling date, actual time, nominal time, deviation from time and concentration by participant, analyte and ethnic group sorted in chronological order
- Phoenix WinNonlin NCA Core Output

In addition, the ratio of PK parameters between the ethnic categories from this study and from historical data from healthy participant studies in non-Asian participants may also be estimated. These integrated analyses across studies will be specified in a separate Integrated Analysis Plan and not included in the CSR.

16.1.6.2 Graphical Summaries and Individual plots (PK Analysis Set)

The following PK plots will be produced based on the PK Analysis Set:

- Overlaid individual concentration versus actual time postdose plots; linear and semi-log; by analyte and ethnic group
- Arithmetic mean concentration time plots; linear with standard deviation and semi-log without standard deviation; using scheduled (nominal) time points by analyte and ethnic group (Japanese, non-Japanese East Asian and overall); if any post-dose concentration is <LLOQ the line representing LLOQ will be added to the semi-log plots
- Boxplots for PK parameters ($AUC_{0-t_{last}}$, $AUC_{0-\infty}$ and C_{max}) by analyte and ethnic group

17 References

Not applicable.

18

Appendices

Not applicable.
